2.1 Rationale for conducting the study

As well as the challenges described above, treatment compliance (persistence and adherence) represents a significant factor affecting the success of treatment (11).

Persistence is defined as the time between initiation and termination of therapy (12). Adherence describes whether patients take their medicine as prescribed. It comprises the initiation, implementation and termination of therapy (13). This compliance can be determined on the basis of the Morisky questionnaire. This consists of questions relating to intake behaviour (14). The questionnaire and its further developed version have already been used for assessing adherence during warfarin therapy, where it exhibited good validity (15, 16).

There are a variety of reasons for poor treatment compliance. These include patient-related aspects (e.g. socioeconomic status, personal convictions), but also disease-related (e.g. symptom severity) and medication-related (e.g. frequency of intake, side effects) aspects (17). This also applies particularly to patients with AF who require permanent oral anticoagulation (18). In terms of anticoagulation for the prevention of strokes, one important aspect is the fact that in the patients' subjective view it does not improve their condition and only the absence of a negative event (e.g. stroke) motivates them to continue treatment. This could limit treatment compliance and reduce the acceptance of side effects.

In addition, it has not yet been elucidated whether omission of the routine monitoring of coagulation status during treatment with dabigatran etexilate and the associated feedback to patients has any effect on treatment adherence in everyday therapeutic use. An analysis of Canadian health insurance data shows that drug persistence following the initiation of everyday care is higher during treatment with dabigatran etexilate than during VKA therapy (19).

No studies have yet been undertaken as to whether there are differences in persistence and adherence within the German care context between patients treated with Pradaxa® or VKA. For this reason, a contribution to the resolution of this question constitutes a relevant gain in knowledge.

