6.2 Details of visits

Visit 1 (start of observation)

- Patient data: sociodemographic data (sex, age, height, weight, education, marital status, health insurance status)
- Case history of non-valvular atrial fibrillation (AF): disease onset, data on disease severity (individual components of the CHA₂DS₂-VASc score) and bleeding risk (individual components of the HAS-BLED score)
- Start of treatment with dabigatran etexilate (110 or 150 mg hard capsules) or VKA (start date)
- Concomitant medication: antiarrhythmics, antihypertensives, lipid-lowering agents, other prescription-only medicines
- Number of other prescription-only and frequency of daily administration (other than dabigatran etexilate/VKA)
- Recording of relevant comorbidities (Charlson et al. 1987)²¹

Visit 2 (after about 3 months of use of dabigatran etexilate or VKA)

- Recording of the continuation of therapy with dabigatran etexilate (including dosage) or VKA since visit 1
- Onset of adverse events since visit 1
- Discontinuation of treatment with dabigatran etexilate or VKA since visit 1
 - Reasons for the discontinuation of treatment with dabigatran etexilate or VKA
 - Antithrombotic therapy after discontinuation of treatment with dabigatran etexilate or VKA
 - In the event of treatment discontinuation, all emergent adverse events (AE) are recorded in the eCRF up to 30 days after the end of therapy.

Visit 3 (after about 6 months of use of dabigatran etexilate or VKA)

BI No.: 1160.218

- Recording of the continuation of therapy with dabigatran etexilate (including dosage) or VKA since visit 2
- Onset of adverse events since visit 2
- Discontinuation of treatment with dabigatran etexilate or VKA since visit 2
 - Reasons for the discontinuation of treatment with dabigatran etexilate or VKA
 - Antithrombotic therapy after discontinuation of treatment with dabigatran etexilate or VKA
 - In the event of treatment discontinuation, all emergent adverse events (AE) are recorded in the eCRF up to 30 days after the end of therapy.
- Regular use of dabigatran etexilate or VKA by means of the Morisky score
- Number of prescription-only medicines and frequency of daily administration
- Recording of disease severity (individual components of the CHA₂DS₂-VASc score) and bleeding risk (individual components of the HAS-BLED score)
- Recording of relevant comorbidities (Charlson et al. 1987)²¹

Visit 4 (after about 9 months of use of dabigatran etexilate or VKA)

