7.3 Planned analyses

The evaluation is performed using SAS® software. All analyses are descriptive. For end-of-text tables, N / mean / SD / min / median / max are given as statistical characterisation measures for constant variables; for categorial variables, N / % per category are given.

All patients documented in the CRF with at least one prescription for dabigatran etexilate or VKA and who meet the inclusion criterion (main diagnosis: non-valvular AF) are included in the analyses (i.e. “all eligible patients”). For the analysis of adverse events, all patients documented in the CRF with at least one prescription for dabigatran etexilate or VKA will be included in the analyses. In order to allow a valid comparison of compliance (persistence and adherence), a 1:1 matching of patients prescribed dabigatran or VKA will be performed based on the exposure propensity score (PS). The propensity score is calculated on the basis of a logistic regression model in which the choice of treatment is included in the model as a dependent variable and further relevant baseline characteristics are considered as independent variables in the model. The relevant baseline characteristics included in the PS model will be predefined in the analysis plan. The choice is based on the premise that all baseline variables for which a priori an association with persistence and/or adherence is expected are to be

included. These variables correspond to the potential confounder variables for a comparative analysis.

Baseline patient characteristics

The cohort resulting from the 1:1 matching as well as the whole cohort of all eligible patients will be characterised, stratified by treatment group, in terms of demographic data, concurrent diseases, concomitant medication, data on AF severity and other baseline characteristics (including risk score for stroke and bleeding, i.e. CHADS-VASc and HAS-BLED).

Persistence and reasons for treatment discontinuation

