The analysis is performed on the basis of the patient cohorts resulting from the 1:1 matching. Kaplan Meier estimates for the time to discontinuation of treatment (cf. definition in section 5.1.) will be calculated separately for the dabigatran and the VKA patient group and illustrated graphically. In particular, the Kaplan Meier estimates for persistence at time 3, 6, 9 and 12 months will be reported. The comparison in terms of the persistence of patients on treatment with dabigatran versus VKA will be performed by means of the stratified log-rank test, which takes account of the dependency of treatment groups resulting from matching (cf. Klein, Moeschberger, 1997, ²²). Patients who discontinued the study prematurely and for whom no treatment discontinuation is documented will be censored at the time of study discontinuation. Patients who end the study as planned will be censored on the day after the last visit if no previous treatment discontinuation is documented.

The absolute number and proportion of patients discontinuing the initial treatment in the course of the study will be summarised overall and according to the reasons for discontinuation for the dabigatran and VKA cohorts.

The association of patient characteristics (including treatment allocation) with persistence will be investigated by means of Cox regression models (univariate and multivariate models). Baseline characteristics will be presented stratified for patients who discontinue the treatment in the course of the study and those who do not.

A multivariable Cox regression model (including the factors used for calculating the PS and choice of treatment) will be reported as a sensitivity analysis. For this analysis, all patients who are within the common supports of the empirical density function of the PS (instead of matched pairs) will be included; the common support is determined after excluding patients with a propensity score above the 97.5% percentile and below the 2.5% percentile in each treatment group in order to avoid a strong influence from patients with extreme PS values.

Adherence

The analysis is performed on the basis of the patient cohort resulting from 1:1 matching. The Morisky questionnaire consists of 8 questions and will be presented at the time of the 6-month visit. The analysis and categorisation of patients into the categories

- poor adherence (score >2)
- medium adherence (score=1, 2) and
- high adherence (score=0)

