7. PLANNED ANALYSIS

All analyses in this study are descriptive; results are to be interpreted in an explorative manner.

For categorical variables summary tabulations of the number and percentage within each category (with a category for missing data) of the parameter will be presented. For continuous variables N, mean, SD, minimum, median, maximum and number of missing values will be presented. To achieve a valid comparability of compliance (persistence and adherence) patients prescribed to dabigatran etexilate or VKA will be matched 1:1 based on the Exposure Propensity Score (PS) and caliper matching with caliper of width equal to 0.2xStandard deviation of PS.

The Propensity Score will be calculated based on a logistic regression model taking the choice of treatment as dependent variable and baseline characteristics as independent variables into account. All baseline variables with an a priori association to persistence and adherence will be included into the regression analysis.

These variables correspond to the potential cofounder variables for a comparative analysis.

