7.4 PRIMARY ENDPOINT(S)

The analysis of the primary endpoint will be based on the patient cohort resulting from the 1:1 matching. Time until termination of treatment will be presented for both treatment groups (Dabigatran etexilate vs. VKA) by Kaplan-Meier estimates and displayed graphically, respectively. Especially for time points 3, 6, 9 and 12 months Kaplan-Meier estimates for persistence will be calculated.

The comparison of persistence between the treatments with dabigatran etexilate versus VKA will be conducted by means of the stratified Log-rank test, which takes dependencies resulting from the matching of the treatment groups into account. Patients who discontinue

study prematurely and without documented treatment discontinuation will be censored at study termination. Patients completing the study as planned will be censored at the day after last visit, if no earlier treatment discontinuation is documented. Association between patient characteristics (incl. method of treatment) and persistence will be determined by means of cox regression (univariate and multivariate model). First, univariate regression for each of the independent variables will be performed. Afterwards, all covariates will be entered into a stepwise multivariate regression. The entry level will be $p=0.5$ and the stay level $p=0.1$. Baseline characteristics will be presented stratified by patients who discontinued the study prematurely versus no discontinuation.

A multivariate Cox Regression model (including factors for the calculation of the propensity score and the choice of treatment) will be used as sensitivity analysis. All patients, who are within the “common support” of the empiric PS density function (instead of the matched pairs), will be included in this analysis. The “common support” will be determined after patients with a propensity score above the 97.5% percentile and below the 2.5% percentile have been excluded for each treatment group, respectively. This will be done to avoid high influence of patients with extreme PS.

The following covariates will be used –depending on the sample size- for the Propensity Score Matching and the sensitivity analysis

- CHA₂DS₂-VASC Score (<2, ≥ 2)
- HAS BLED-Score (<3, ≥ 3)
- Age at registration (<65, 65-<75, ≥ 75)
- Previous stroke (Yes, No)
- Treatment (VKA, Pradaxa[®]) (sensitivity analysis only)

and the following covariates will be used –depending on the sample size- for the Cox regression

- CHA₂DS₂-VASC Score (<2, ≥ 2)

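### The propensity score list in SAP 7.4 omits education and health insurance status, although the plan's own inclusion rule and Protocol 2.1 point to them, and the visible text gives no reason

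*SAP*

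**What the plan says.** Protocol 7.3 leaves the choice of covariates to the SAP: "The relevant baseline characteristics included in the PS model will be predefined in the analysis plan". It also sets the rule for that choice, namely that the score is to contain "all baseline variables for which a priori an association with persistence and/or adherence is expected". SAP 7 repeats the rule: "All baseline variables with an a priori association to persistence and adherence will be included into the regression analysis". SAP 4 records no change to the planned analysis.

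SAP 7.4 then gives one list "for the Propensity Score Matching and the sensitivity analysis": CHA₂DS₂-VASc (<2, ≥2), HAS-BLED (<3, ≥3), age in three bands, and previous stroke. Treatment is added for the sensitivity model only. Use of the list is made conditional on the sample size, with no rule for what would change.

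On what is expected to affect compliance, Protocol 2.1 says: "These include patient-related aspects (e.g. socioeconomic status, personal convictions", and it also mentions frequency of intake. Protocol 6.2 collects at visit 1 "sociodemographic data (sex, age, height, weight, education, marital status, health insurance status" and "Number of other prescription-only and frequency of daily administration (other than dabigatran etexilate/VKA". SAP 5.4 lists education and health insurance among the other variables.

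For the sensitivity Cox model, Protocol 7.3 prescribes a model "including the factors used for calculating the PS and choice of treatment".

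**The concern.** The primary objective is a comparison of persistence between two treatments that the physician chooses. Protocol 7.1 expects the two groups to differ for that reason, and matching on the score is the plan's main remedy. The list in SAP 7.4 does not follow the rule that was meant to produce it. A determinant the protocol names is left out, although two measures of it are collected.

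Nothing later in the plan would catch the consequence. The sensitivity model adjusts for the same four factors. The exploratory Cox list adds only physician specialty. SAP 7.1 tabulates baseline characteristics in the matched cohort, but no step follows if an imbalance shows. If education or insurance status also influenced which drug was prescribed, both the persistence and the adherence comparison would carry that difference unadjusted.

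**Working it through.** **1. Rule against list.**

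| Step | Source | Content |
|---|---|---|
| Rule | Protocol 7.3; SAP 7 | all baseline variables with an expected association with persistence/adherence |
| Expected determinant | Protocol 2.1 | socioeconomic status, as a reason for poor compliance (there: persistence and adherence) |
| Collected | Protocol 6.2; SAP 5.4 | education, health insurance status |
| In the score | SAP 7.4 | two risk scores, age, previous stroke |
| Declared change | SAP 4 | none |

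The SAP joins persistence and adherence with *and*, where the protocol has *and/or*. This makes no difference here, because Protocol 2.1 uses compliance for both.

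**2. The plan's own figures (Local Amendment 1, Change 3).** Matched patients: 2 × 0.66 × 800 = 1056, which reproduces.

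Power, with exponential times and 15% drop-out at one year:
- Event probability at persistence p: q(p) = λ/(λ+γ) × (1 − 0.85p), with λ = −ln p and γ = −ln 0.85 = 0.1625.
- q(0.63) = 0.344 and q(0.538) = 0.430, so 528 pairs give 528 × 0.774 ≈ 408 events.
- HR = ln 0.63 / ln 0.538 = 0.745.
- Power = Φ(½√events × |ln HR| − 1.96) = 84.4%, against 84.8% stated.

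At 51% the same formula gives 97.2% (97.8% stated). At 56.5% it gives 55.7% (61.1% stated). That last difference is a separate matter and is not used here.

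**3. Does sample size force the short list?** The four covariates use 1 + 1 + 2 + 1 = 5 slopes, so 800/5 = 160 patients per arm per slope. With 10 slopes the figure is 80, and with 15 it is 53. The planned size leaves room.

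**4. Possible size of bias (all inputs assumed).** One binary factor, independent of the listed covariates; prevalence π = 0.3 or 0.5; half the patients on each drug; odds ratio (OR) of 1.2 to 2 for treatment choice; discontinuation hazard ratio h of 1.3 or 1.5; no true treatment effect.
- Find a so that (1−π)·expit(a) + π·expit(a + ln OR) = 0.5. Then π₁ = 2π·expit(a + ln OR) and π₀ = 2π − π₁ are the factor's prevalences in the two arms.
- 12-month persistence in arm t: S_t = (1−π_t)e^(−λ) + π_t e^(−λh), with λ here the yearly hazard without the factor, set so that S₀ = 0.63.
- Smallest case (π 0.3, OR 1.2, h 1.3): π₁ = 0.319, π₀ = 0.281, λ = 0.428, S₁ = 0.627, gap 0.3 points.
- Largest case (π 0.5, OR 2, h 1.5): π₁ = 0.586, π₀ = 0.414, λ = 0.387, S₁ = 0.6095, gap 2.05 points.

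| OR for treatment choice | gap in points, h = 1.3 | gap in points, h = 1.5 |
|---|---|---|
| 1 | 0 | 0 |
| 1.2 | 0.30–0.35 | 0.47–0.54 |
| 1.5 | 0.67–0.77 | 1.05–1.20 |
| 2 | 1.13–1.32 | 1.78–2.05 |

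The spurious HR, approximately (1 + π₁(h−1))/(1 + π₀(h−1)), runs from 1.01 to 1.07. The planned differences are 63 − 56.5 = 6.5, 63 − 53.8 = 9.2 and 63 − 51 = 12 points. A factor correlated with age or the risk scores would bias less, because matching removes part of its imbalance.

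**5. Price of fewer pairs (assumed losses), at 63% vs 53.8%.** 528 pairs: 84.4%. 475 pairs (−10%): 80.4%. 422 pairs (−20%): 75.7%.

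**The case against.** The protocol lets the SAP choose the covariates, and Protocol 2.1 is general background that names neither education nor insurance. That stands in part: the two are the nearest collected measures, which is an inference. But the freedom to choose comes with a rule, and a list that leaves the named determinant unrepresented needs a reason.

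A reader might infer that the sponsor gave no reason at all. The documents do not support that, because SAP sections 6.4 and 9 are not in the text available. The SAP was also finalised after the target fell from 4000 to 1600, which may explain a short list. The sample-size condition itself concerns the listed covariates and does not explain leaving others out.

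The design helps. Patients must be eligible for both drugs, and each physician alternates between them, so socioeconomic differences between practices should be largely balanced. Differences between patients of the same practice remain, and nothing in the plan addresses them.

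The analyses are declared descriptive and exploratory. That limits what is claimed from a p-value but does not remove confounding from a comparison the plan wants to be valid.

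Two further readings are tempting. One is that the sensitivity model departs from the protocol; it does not, since Protocol 7.3 prescribes the same factors. The other is that categorised covariates are an error; no rule in the documents forbids them, and the effect of the categories has not been quantified.

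**Conclusion.** The point holds as an inconsistency within the plan: the score omits collected measures of a determinant the protocol itself names, the visible text does not say why, and neither the sensitivity model nor the baseline tables would lead to a correction. It should be fixed before the analysis.

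A reader might go further and infer that the primary comparison is biased. The documents do not support that. Confounding also needs a link between these variables and the choice of drug, and no section states one; Protocol 7.1 expects group differences only in general. Size and direction therefore cannot be derived. Under the assumptions above, one omitted factor shifts the 12-month difference by about 0.3 to 2 points, clearly less than the smallest planned difference of 6.5. Two independent factors could reach 4.0 points, but only if both have 50% prevalence, an OR of 2 and a hazard ratio of 1.5 in the same direction. Two equal factors in opposite directions would cancel.

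**What to change.** In SAP 7.4:
- Add education and health insurance status to the propensity score and to the common-support sensitivity Cox model. Keep patients with missing values through a Missing level, in line with SAP 6.6.
- Add a closed list of the other visit-1 variables the sponsor expects to be associated with persistence. Candidates are sex, marital status, and the number and daily frequency of other prescription medicines. Give a reason for any candidate left out.
- Delete the sample-size condition for these two models.
- Check covariate balance in the matched cohort before the outcome analysis, and report a comparison adjusted for any covariate that remains imbalanced.

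Continuous age and separate score components are optional. Items that are nearly empty in newly treated patients, such as labile INR, should not be entered separately.

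The cost is SAP wording, programming and a few more parameters; the variables are already collected. The drawback is possibly fewer matched pairs. That loss is unknown, because 528 pairs is a planning assumption and not the yield of the present list. If pairs fell 10% or 20% below 528, power at 63% vs 53.8% would drop from about 84% to about 80% or 76%.

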2. LIST OF ABBREVIATIONS

Term	Definition / description
AE	Adverse event
AF	Atrial fibrillation
CHA ₂ DS ₂ -VASc-Score	Congestive heart failure, Hypertension, Age (>75), Diabetes mellitus, Stroke/TIA, Vascular disease, Age 65-74, Sex category
CTCAE	Common Terminology Criteria for Adverse events
CTP	Clinical Trial Protocol
FAS	Full Analysis Set
HAS-BLED	Hypertension, Abnormal renal and liver function, Stroke (1 point), bleeding history or predisposition, Labile INR, Elderly (>65 years), Drug and Alcohol
INR	International Normalized Ratio
MedDRA	Medical Dictionary or Regulatory Activities
MG	Matched Group
N	Number
NCI-CTCAE	National Cancer Institute-Common Terminology Criteria for Adverse events
PS	Propensity Score
PT	Preferred Term
SAE	Serious Adverse event
SD	Standard Deviation
SOC	System Organ Class
SUSAR	Suspected Unexpected Serious Adverse Reaction
TS	Treated Set
TSAP	Trial statistical analysis plan
VKA	Vitamin-K-Antagonists
WHO-DD	World Health Organization Drug dictionary

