- HAS BLED-Score (<3, ≥ 3)
- Age at registration (<65, 65-<75, ≥ 75)
- Previous stroke (Yes, No)
- Medical specialty of attending physician (Internist, Cardiologist, General practitioner, Other)
- Treatment (VKA, Pradaxa[®]).

Additionally, the following subgroups will be presented for persistence (overall and for each treatment group):

- CHA₂DS₂-VASC-Score (<2, ≥ 2)
- Age (<65, 65- <75, ≥ 75)
- Previous stroke (Yes, No)
- Medical specialty of attending physician (Internist, Cardiologist, General practitioner, Other)
- Daily dose of Pradaxa[®] at initial visit (2x110mg daily, 2x150mg daily) [Patients treated with Pradaxa[®] only]
- HAS-BLED-Score (<3, ≥ 3).

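### The multivariable Cox model of factors for persistence enters the CHA2DS2-VASc category beside age band and previous stroke, which are parts of that score, so its age coefficient can show a false effect in either direction

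*SAP*

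**What the plan says.** SAP 7.4 describes the model's purpose: "Association between patient characteristics (incl. method of treatment) and persistence will be determined by means of cox regression (univariate and multivariate model". Each covariate is fitted alone first. All then go into a stepwise multivariable model with entry at p=0.5 and stay at p=0.1. Subject to sample size, the covariates are "CHA₂DS₂-VASC Score (<2, ≥ 2", HAS-BLED (cut at 3), "Age at registration (<65, 65-<75, ≥ 75", "Previous stroke (Yes, No", physician specialty and treatment.

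The SAP list of abbreviations gives the content of the two scores. CHA2DS2-VASc is "Congestive heart failure, Hypertension, Age (>75), Diabetes mellitus, Stroke/TIA, Vascular disease, Age 65-74, Sex category". HAS-BLED is "Hypertension, Abnormal renal and liver function, Stroke (1 point), bleeding history or predisposition, Labile INR, Elderly (>65 years), Drug and Alcohol". Age and stroke are in both, and the SAP does not comment on the overlap.

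Protocol 6.2 has visit 1 record the CHA2DS2-VASc items one by one, and likewise "bleeding risk (individual components of the HAS-BLED score".

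**The concern.** A coefficient in a multivariable model is read as the effect of that factor with the others held constant. Here one of the others is a category partly made of age and stroke. Holding it constant compares patients aged 75 or over, who reach the category by age alone, with younger patients who reached it through comorbidity.

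At stake are the adjusted age and stroke hazard ratios in a factor analysis promised in Protocol 7.3 and SAP 7.4. A reader could take an age effect as real when it partly measures hypertension, diabetes, heart failure or vascular disease.

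**Working it through.** The documents give no figure for this model, so there is none to reproduce.

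**Step 1. What age and stroke force.** The point weights are not tabulated. From the subscripts in the score's name I assume 2 points each for the upper age class and for stroke, and 1 for every other item. The list writes >75 and 65-74; I place age 75 in the upper class, as the SAP's age bands do. Possible totals:

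| Age | No stroke | Stroke |
|---|---|---|
| <65 | 0 to 5 | 2 to 7 |
| 65-74 | 1 to 6 | 3 to 8 |
| ≥75 | 2 to 7 | 4 to 9 |

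The category is forced to ≥2 by age ≥75 or by stroke. In the other two cells it is open: 39% to 69% of patients under 65 without stroke, and 81% to 96% of those aged 65-74, are at ≥2 under the two prevalence sets used below.

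**Step 2. Who is compared within ≥2.** Take patients without stroke and without the sex point, with independent components at the same prevalence in every age band. N is the number of heart failure, hypertension, diabetes and vascular disease present. Reaching ≥2 requires N≥2 under 65, N≥1 at 65-74, and nothing at ≥75.

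- Low set (10%, 50%, 15%, 10%): E[N] = 0.85, P(N=0) = 0.9×0.5×0.85×0.9 = 0.344, P(N=1) = 0.4815. Mean N within ≥2: under 65, (0.85−0.4815)/(1−0.344−0.4815) = 2.11; 65-74, 0.85/0.656 = 1.30; ≥75, 0.85.
- High set (25%, 80%, 28%, 25%): E[N] = 1.58, P(N=0) = 0.081, P(N=1) = 0.4095. Mean N within ≥2: (1.58−0.4095)/0.5095 = 2.30; 1.58/0.919 = 1.72; 1.58.

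Within the category, younger patients carry more comorbidity. Put differently, the model applies the category's hazard ratio to every patient aged ≥75, and the age coefficient has to take the excess back.

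**Step 3. Size in the full model, without stepwise selection.** From the plan: 1056 matched patients, 15% drop-out and the persistence assumptions (Amendment 1). Assumed: age mix, prevalences, component effects, and true hazard ratios of 1 for age and stroke. Hazard ratios come from 200,000 simulated patients and error rates from 1000 trials. The error column is for age ≥75 at two-sided 0.05 in one direction, nominal 2.5%.

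| Prevalence set | HR per component | HR age ≥75 | HR stroke | False result |
|---|---|---|---|---|
| High | 0.7 | 1.156 | 1.046 | 15.7% harmful |
| High | 1.0 | 1.005 | 0.991 | 2.8% protective |
| High | 1.15 | 0.955 | 0.989 | 5.5% protective |
| High | 1.3 | 0.929 | 0.974 | 11.3% protective |
| High | 1.5 | 0.883 | 0.951 | 15.2% protective |
| Low | 0.7 | 1.199 | 1.089 | 23.8% harmful |
| Low | 1.0 | 1.008 | 0.989 | 2.3% protective |
| Low | 1.15 | 0.918 | 0.971 | 9.5% protective |
| Low | 1.3 | 0.854 | 0.922 | 17.9% protective |
| Low | 1.5 | 0.803 | 0.897 | 32.2% protective |

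With the components entered separately, the hazard ratio for age ≥75 is 0.988 to 1.015 in all ten rows, and it is falsely protective in 2.1% to 3.6% of trials. A separate simulation gave 0.81 to 0.94 (comorbidities raising the hazard) and 1.18 to 1.21 (lowering it), against 0.98 to 1.02 with components.

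**Step 4. With the planned stepwise rule (n=1056).**

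- Hypertension 75%, diabetes 25%, heart failure and vascular disease 20% each, specialty omitted, 300 runs: age ≥75 at p<0.05 in 4%, 5% and 19% of runs for component HRs of 1.15, 1.3 and 1.5. The full model gave 6%, 10% and 25%; nominal is 5%.
- High and low sets, age as one class term, 600 runs: age kept with a falsely protective coefficient in 10% and 19% (high) or 13% and 24% (low) for component HRs of 1.3 and 1.5. About 5% is expected at the stay level. With components it is 3% to 5%.
- A third set of runs gave 5% to 28% at p<0.05 over component HRs of 1.15 to 1.5, near nominal at 1.15.

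**Step 5. HAS-BLED.** Stroke counts one point; if older age also counts one, the two together do not reach the cut of 3, so nothing is forced. In the low-set runs that dropped only the CHA2DS2-VASc category (component HRs 0.7, 1.0 and 1.15), the hazard ratio for age ≥75 was 0.997 to 1.004. Nearly all the bias comes from CHA2DS2-VASc.

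**The case against.** The case for leaving the SAP as it is has substance.

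- A reader might infer that age and stroke determine the score, so that the model cannot be estimated. They do not: the total is open in every cell, the category is forced one way only, and the model has full rank. The difficulty is one of interpretation.
- A reader might expect a false protective effect of age. The documents give no comorbidity effects on discontinuation, so the direction is unknown, and without such effects there is no bias.
- The full-model error rates are not those of the planned procedure. Stepwise selection often drops age or the score, and at a component HR of 1.15 the false-positive rate is near nominal. At 1.3 the simulations disagree (5% against a nominal 5%, or 10% to 13% against an expected 5%). At 1.5 all show inflation.
- Univariate age models and subgroup tables by age and stroke are already planned. The univariate hazard ratio for age ≥75 was 0.98 to 1.03 in simulation, with 5% to 6% false positives. These results stand beside the multivariable ones but are unadjusted, so they do not replace them.
- All analyses are declared descriptive and exploratory (Protocol 7, SAP 7), and a coefficient conditional on the score category is a legitimate quantity if read as such. That lowers the priority. It does not help someone who reads the adjusted hazard ratio as an age effect.

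**Conclusion.** The point holds as an improvement to the multivariable factor model. With no true age effect, the full model gives a hazard ratio for age ≥75 of about 0.80 to 0.96 when each comorbidity raises discontinuation with a hazard ratio of 1.15 to 1.5, and about 1.16 to 1.21 when it is 0.7. The stroke coefficient moves in the same direction by less. The planned selection rule leaves inflated false positives only for the stronger comorbidity effects.

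The sizes rest on the assumed point weights, prevalences, age mix and comorbidity effects. The one-way forcing rests only on the weights and on where age 75 is placed.

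It would be wrong to infer that the primary result is in doubt. The log-rank comparison in matched pairs does not use this model, and in the propensity score the individual coefficients are not interpreted. Low priority.

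**What to change.** In the SAP 7.4 multivariable association model only, replace the CHA2DS2-VASc category by its remaining components (heart failure, hypertension, diabetes, vascular disease, sex) beside age band and previous stroke. Leave the HAS-BLED category out, or replace it by the items that do not overlap. Keep both score categories in the univariate models and subgroup tables.

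The cost is SAP wording, with no new data. The planned model has 9 parameters (two scores 2, age 2, stroke 1, specialty 3, treatment 1). Swapping one score term for five components gives 13, or 12 without HAS-BLED. Splitting HAS-BLED would add about four to six to the 12.

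Expected events, assuming 58.5% overall persistence at 12 months and exponential drop-out of 15%: the hazards are −ln 0.585 = 0.536 and −ln 0.85 = 0.163, so the event probability is (0.536/0.699)×(1−0.585×0.85) = 0.386, and 1056×0.386 ≈ 407. That is about 31 events per parameter with 13 parameters and about 23 with 18.
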